### **Reporting SAEs using commercially available drugs**

In addition, any unexpected (not listed in the package insert) and serious adverse events that are related (definitely, probably or possibly related) with the use of pembrolizumab/nivolumab, it must be reported to the FDA within 10 business days using a FDA Form MedWatch 3500 form <http://www.fda.gov/medwatch/safety/3500.pdf> (fax # [name]).

### **Reporting SAEs for Investigational Agent Trigriluzole**

The PI shall notify the FDA of any adverse experience related to the use of trigriluzole or the combination of pembrolizumab/nivolumab + trigriluzole that is both serious and unexpected, as soon as possible and in no event later than 15 calendar days after the PI's discovery of the event. Each written notification may be submitted on FDA Form MedWatch 3500A <http://www.fda.gov/medwatch/safety/3500a.pdf> (fax # [name]).

The PI shall also notify the FDA by telephone or by facsimile transmission of any unexpected fatal or life-threatening experiences associated with the use of trigriluzole or the combination of pembrolizumab/nivolumab + trigriluzole, as soon as possible but no later than 7 calendar days from the PI's discovery of the event information.

### **Definitions**

#### **Definition of SAE**

A serious adverse event (SAE) is one occurring at any dose level that results in any of the following outcomes:

- Death
- Life-threatening- immediate risk of death from the reaction.
- Requires inpatient hospitalization or prolongation of existing hospitalization.
- Results in persistent or significant disability/incapacity.
- Results in a congenital anomaly/birth defect.
- Requires intervention to prevent one of the outcomes listed in this definition.

The definition of serious adverse event (experience) also includes *important medical events*. Medical and scientific judgment will be exercised in deciding whether expedited reporting is appropriate in other situations, such as important medical events that may not be immediately life-threatening or result in death or hospitalization but may jeopardize the patient or may require intervention to prevent one of the other outcomes listed in the definition above. These events will usually be considered serious. Examples of such events

are intensive treatment in an emergency room or at home for allergic bronchospasm; blood dyscrasias or convulsions that do not result in hospitalization.

### **Definition of Related**

There is a reasonable possibility that the drug caused the adverse experience. That is, the event is judged by the investigator to be possibly, probably or definitely related to the treatment.

### **Definition of Unexpected**

Any adverse drug experience and/or specificity, that is not included in the current investigator's brochure and/or package insert.

## **1.7.12 TREATMENT EVALUATION/CRITERIA FOR RESPONSE**

### **RECIST and Modified RECIST Definition**

#### **RECIST**

Response and progression will be evaluated in this study using the revised international criteria called RECISTv1.1 proposed by the Response Evaluation Criteria in Solid Tumors (RECIST) Committee. RECIST v1.1 criteria will be **modified** for this protocol to include a stipulation that PD must be confirmed to account for pseudoprogression (tumor flare phenomenon). The first instance of PD must be confirmed by either:

- 1) confirmation of disease progression by repeat assessment 4-12 weeks later OR
- 2) association with clinical deterioration (such as a significant decline in performance status).

Changes in only the largest diameter (unidimensional measurement) of the tumor lesions are used in the RECIST criteria. Note: Lesions are either measurable or non-measurable using the criteria provided below. The term "evaluable" in reference to measurability will not be used because it does not provide additional meaning or accuracy.

#### **Timing of Assessments**

For the purposes of this study, patients should be evaluated at baseline and then reevaluated for response at Week 7, Week 13, and then every 12 weeks thereafter per the Study Calendar. Confirmatory scans should be obtained not less than 4 weeks following

initial documentation of objective response or progressive disease (PD). If a subject has discontinued active treatment due to reasons other than PD, the subject will continue to have CT scans Q12 weeks until Week 49 (window can be widened to  $\pm 28$  days).

### **Measurable Disease**

Measurable lesions are defined as those that can be accurately measured in at least one dimension (longest diameter to be recorded) as  $>20$  mm with conventional techniques (CT, MRI, x-ray) or as  $>10$  mm with spiral CT scan. All tumor measurements must be recorded in millimeters (or decimal fractions of centimeters).

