### **Non-Measurable Disease**

All other lesions (or sites of disease), including small lesions (longest diameter  $<20$  mm with conventional techniques or  $<10$  mm using spiral CT scan), are considered non-measurable disease. Bone lesions, leptomeningeal disease, ascites, pleural/pericardial effusions, lymphangitis cutis/pulmonis, inflammatory breast disease, abdominal masses (not followed by CT or MRI), and cystic lesions are all non-measurable.

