### **Target Lesions**

All measurable lesions up to a maximum of 2 lesions per organ and 5 lesions in total, representative of all involved organs, will be identified as target lesions and recorded and measured at baseline. Target lesions will be selected on the basis of their size (lesions with the longest diameter) and their suitability for accurate repeated measurements (either by imaging techniques or clinically). A sum of the longest diameter (LD) for all target lesions will be calculated and reported as the baseline sum LD. The baseline sum LD will be used as reference by which to characterize the objective tumor response. There may be occasions when progressive disease is suspected but cannot be fully characterized. In these cases the treating physician may decide to continue treatment for one or two cycles before reassessment, if he/she feels it is in the patients' best interest and the patient agrees to continue treatment.

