### RECIST Response Categories

#### Evaluation of Target Lesions

Complete Response (CR):	Disappearance of all target lesions
Partial Response (PR):	At least a 30% decrease in the sum of the longest diameter (LD) of target lesions, taking as reference the baseline sum LD.
Progressive Disease (PD):	At least a 20% increase in the sum of the LD of target lesions, taking as reference the smallest sum LD recorded since the treatment started or the appearance of one or more new lesions. In addition to the relative increase of 20%, the sum must also demonstrate an absolute increase of at least 5 mm. (Note: the appearance of one or more new lesions is also considered progression).
Stable Disease (SD):	Neither sufficient shrinkage to qualify for PR nor sufficient increase to qualify for PD, taking as reference the smallest sum LD since the treatment started.

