#### Evaluation of Non-Target Lesions

Complete Response (CR):	Disappearance of all non-target lesions and normalization of tumor marker level. All lymph nodes must be non-pathological in size (<10mm short axis).
Non-CR/Non-PD	Persistence of one or more non-target lesion(s) and/or maintenance of tumor marker level above the normal limits.

Progressive Disease (PD):	Unequivocal progression of existing non-target lesions. (Note: the appearance of one or more new lesions is also considered progression).
	Although a clear progression of “non-target” lesions only is exceptional, in such circumstances the opinion of the investigator will prevail.
*Note: If tumor markers are initially above the upper normal limit, they must normalize for a patient to be considered in complete clinical response.	

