### **Inclusion Criteria**

A patient/subject is eligible for enrollment if *all* of the following inclusion criteria are met.

- 1) Patients must have histologically confirmed solid malignancy or lymphoma that is metastatic or unresectable
- 2) There is reasonable expectation of response to pembrolizumab or nivolumab, and one of the drugs is available from the commercial supply. This includes (but is not limited to) the following tumor types: melanoma, non-small cell lung cancer, renal cell carcinoma, squamous cell carcinoma of the head and neck, bladder cancer, and classic Hodgkin lymphoma.
- 3) The patient must have failed at least one line of standard treatment, with the following exceptions in which a PD-1 antibody is FDA approved in the first-line setting:
  - a. melanoma patients
  - b. non-small cell lung cancer patients without EGFR or ALK genomic tumor aberrations whose tumors have high PD-L1 expression [(Tumor Proportion Score (TPS)  $\geq 50\%$ )] as determined by an FDA-approved test.
- 4) Age  $\geq 18$  years old
- 5) Patients must give informed consent.
- 6) Prior chemotherapy, immunotherapy, radiotherapy or major surgery (including radiation therapy or surgery for treatment of brain metastases) must be

completed at least 3 weeks before study entry. Prior PD-1 or PD-L1 therapy is acceptable.

- 7) Patients must have an ECOG performance status  $\leq 2$  (Appendix A).
- 8) Patients must have normal organ and marrow function as defined below:
  - a. Hemoglobin  $>8.0$  mg/dL (without transfusion in the preceding 7 days)
  - b. Platelets  $\geq 70,000$  / $\mu$ L
  - c. Total bilirubin within normal institutional limits (patients with Gilbert's Syndrome must have a total bilirubin  $< 3.0$  mg/dL).
  - d. AST(SGOT)  $<2X$  institutional ULN
  - e. ALT(SGPT)  $<2X$  institutional ULN
- 9) Patients must have measurable disease, defined as at least one lesion that can be accurately measured in at least one dimension (longest diameter to be recorded) as  $\geq 10$  mm by CT scan, PET/CT scan, MRI or caliper/ruler measurement by clinical exam. Lymph nodes: to be considered pathologically enlarged and measurable, a lymph node must be  $\geq 15$  mm in short axis when assessed by CT scan. Lesions that have been radiated in the advanced setting cannot be included as sites of measurable disease unless clear tumor progression has been documented in these lesions since the end of radiation therapy.
- 10) Ability to swallow pills

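### A sole lesion of 10–20 mm on MRI or conventional CT admits a subject who then has no target lesion and cannot be scored PR; nodes also change axis between eligibility and response

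*Combined protocol and SAP*

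**What the plan says.** - **Eligibility** (section 4.1.1, inclusion criterion 9): at least one lesion of 10 or more "mm by CT scan, PET/CT scan, MRI or caliper/ruler measurement by clinical exam". A lymph node counts from 15 "mm in short axis when assessed by CT scan".
- **Measurability for response** (section 1.7.12, Measurable Disease): more than 20 mm longest diameter "with conventional techniques (CT, MRI, x-ray", or more than 10 "mm with spiral CT scan". Non-Measurable Disease takes in the rest: "All other lesions (or sites of disease), including small lesions".
- **Target selection and sum** (section 1.7.12, Target Lesions): targets come only from measurable lesions. "A sum of the longest diameter (LD) for all target lesions will be calculated", with no separate rule for nodes. The RECIST subsection likewise relies on the largest diameter alone.
- **Complete response** (section 1.7.12): the target table requires "Disappearance of all target lesions". A nodal size rule appears only in the non-target table: "All lymph nodes must be non-pathological in size (<10mm short axis".
- **Denominator** (section 6.1, Definitions of Evaluable for Toxicity and Response): one on-study tumor assessment makes a subject evaluable for response. A target lesion is not required.
- **Declared departures** (section 1.7.12, RECIST): RECIST v1.1 is the named standard, and confirmation of PD is the only modification stated.

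**The concern.** One term carries two definitions. The first decides who enters; the second decides who has a target lesion. In the table under Evaluation of Best Overall Response, every row leading to CR, PR or SD needs a target-lesion category. A subject admitted under the first definition but not measurable under the second has no such category, so PR is out of reach, yet the subject stays in the ORR denominator. The difference is not declared as intended. Section 1.8 (Tumor Sampling) also discusses RECIST target lesions under 2 cm, a size at which Measurable Disease accepts imaging lesions only on spiral CT.

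The nodal rules add a second inconsistency. Short axis governs entry and the nodal size rule for CR, while longest diameter governs the sum. Lymphoma is eligible, so disease confined to nodes is foreseeable. Two assessors reading the same scans could assign different responses, depending on which subsection they follow.

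**Working it through.** The plan gives no figure to reproduce here, so the check sets the rules side by side and then sizes the effect.

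**1. Size thresholds, subject with one non-nodal lesion (longest diameter)**

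| Modality | Criterion 9 | Section 1.7.12 | Eligible but not measurable |
|---|---|---|---|
| MRI or conventional CT | ≥10 mm | >20 mm | 10 to 20 mm inclusive |
| Spiral CT | ≥10 mm | >10 mm | exactly 10 mm |
| PET/CT | ≥10 mm | not named | threshold undefined |
| Caliper/ruler | ≥10 mm | superficial lesions measurable, no size given | threshold undefined |

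The first row can occur, because Guidelines for Evaluation of Measurable Disease allows conventional CT and MRI.

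**2. Size thresholds, subject with one node**

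- Conventional CT, assumed node 15 mm (short axis) × 20 mm (longest diameter): eligible, since 15 ≥ 15; not measurable, since 20 is not above 20.
- Spiral CT: every eligible node is measurable, because its longest diameter is at least 15 mm.
- In reverse, an assumed 9 × 22 mm node passes both imaging limits of section 1.7.12 (22 > 20). Yet it is below the 15 mm entry rule and within the size that the non-target table treats as non-pathological.

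**3. Nodal axis and percent change**

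Change = (follow-up − baseline) / baseline; PR needs a fall of at least 30%. Assumed sole target node, 16 × 25 mm shrinking to 12 × 17 mm:

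- longest diameter: (17 − 25)/25 = −32%, PR
- short axis: (12 − 16)/16 = −25%, SD

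The choice of axis can therefore change ORR.

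**4. Wording of target CR**

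Assumed sole target node, 16 × 25 mm shrinking to 8 × 12 mm: longest diameter (12 − 25)/25 = −52%. The node is still visible, so the target table gives PR, while its 8 mm short axis meets the nodal size rule in the non-target table. Both CR and PR count as objective responses. On short axis this holds generally: an eligible node going from at least 15 mm to under 10 mm falls by more than (15 − 10)/15 = 33%, so PR is already met. If longest diameter is kept, a normalized node might fall by less than 30% on that axis; that is the axis problem of step 3 again.

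**5. Weight of one subject in ORR**

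Planned enrolment is 12–27 (section 4.1.4). One subject is 1/12 = 8.3 points or 1/27 = 3.7 points. With assumed responder counts and exact (Clopper-Pearson) intervals at the 90% level named in Analysis Plan for Secondary Endpoints:

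- N=12: 3/12 = 25.0% (7.2–52.7%) versus 4/12 = 33.3% (12.3–60.9%)
- N=27: 7/27 = 25.9% (12.9–43.2%) versus 8/27 = 29.6% (15.7–47.1%)

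**The case against.** The strongest reply is that little turns on this. A subject is caught by the size gap only if no other lesion is measurable. If all imaging is spiral CT, the gap shrinks to exactly 10 mm, which may be no more than a missing equals sign. ORR is summarized descriptively, and one subject's shift is small beside the intervals above. All of that stands as a limit on size. It does not remove the contradiction: the protocol does not require spiral CT, and the nodal conflict does not depend on scanner type.

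Three stronger readings might be inferred, and the documents do not support them.

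- *That a 10–20 mm caliper lesion leaves a subject without a target.* The 20 mm limit names CT, MRI and x-ray. The Guidelines subsection treats superficial clinical lesions as measurable without a size, and Target Lesions allows clinical follow-up.
- *That affected subjects cannot be classified at all.* Non-target categories exist, and non-target progression or a new lesion gives overall PD whatever the target status. What is lost is the route to PR.
- *That the CR wording lowers ORR.* Taken on its own it moves a subject between CR and PR.

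It can also be argued that the nodal CR rule, worded for all nodes, already covers target nodes. That is a possible reading, but the rule sits in the non-target table and conflicts with the target table, so the plan needs to say so.

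**Conclusion.** The plan is wrong as written on measurability. Section 1.7.12 contradicts inclusion criterion 9, and a subject whose only lesion is 10–20 mm on MRI or conventional CT is eligible, counts toward the ORR denominator once assessed, and cannot be scored PR. The nodal axis is a separate inconsistency that can change percent change and PR versus SD. The nodal CR wording is an ambiguity that bears on CR versus PR.

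The number of affected subjects is unknown. Any percentage for their share would be an assumption, since the documents give neither lesion sizes nor the mix of imaging methods. Each affected subject is worth 3.7 (N=27) to 8.3 (N=12) points of ORR, taking all enrolled subjects as evaluable. The lesion sizes and responder counts used above are illustrations. Only secondary, descriptive efficacy endpoints are touched; MTD/RP2D is not.

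**What to change.** In section 1.7.12:

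1. Under Measurable Disease and Non-Measurable Disease, replace the CT, MRI, PET/CT and caliper thresholds with those of inclusion criterion 9, using the same inequality sign in both places.
2. Keep a stated threshold for chest x-ray lesions. Criterion 9 has none, but the Guidelines subsection accepts such lesions as measurable, so copying criterion 9 alone would open a new gap.
3. Use one nodal axis for eligibility and for the target sum, and amend the largest-diameter statements under RECIST and Target Lesions to match. Short axis is the consistent choice, because criterion 9 and the nodal CR rule already use it.
4. State in the target table that the rule of under 10 mm short axis also applies to nodal targets for CR.

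The cost is a text edit plus some possible re-reading. Nodes already recorded by longest diameter may need their short axes measured from existing images. No new scans or visits are needed.

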### **Non-Measurable Disease**

All other lesions (or sites of disease), including small lesions (longest diameter  $<20$  mm with conventional techniques or  $<10$  mm using spiral CT scan), are considered non-measurable disease. Bone lesions, leptomeningeal disease, ascites, pleural/pericardial effusions, lymphangitis cutis/pulmonis, inflammatory breast disease, abdominal masses (not followed by CT or MRI), and cystic lesions are all non-measurable.

### **Target Lesions**

All measurable lesions up to a maximum of 2 lesions per organ and 5 lesions in total, representative of all involved organs, will be identified as target lesions and recorded and measured at baseline. Target lesions will be selected on the basis of their size (lesions with the longest diameter) and their suitability for accurate repeated measurements (either by imaging techniques or clinically). A sum of the longest diameter (LD) for all target lesions will be calculated and reported as the baseline sum LD. The baseline sum LD will be used as reference by which to characterize the objective tumor response. There may be occasions when progressive disease is suspected but cannot be fully characterized. In these cases the treating physician may decide to continue treatment for one or two cycles before reassessment, if he/she feels it is in the patients' best interest and the patient agrees to continue treatment.

### **Non-Target Lesions**

All other lesions (or sites of disease) will be identified as non-target lesions and will be recorded at baseline. Non-target lesions include measurable lesions that exceed the maximum numbers per organ or total of all involved organs as well as non-measurable lesions. Measurements of these lesions are not required, but the presence or absence of each will be noted throughout follow-up.

## Guidelines for Evaluation of Measurable Disease

All measurements will be taken and recorded in metric notation using a ruler or calipers. All baseline evaluations will be performed as closely as possible to the beginning of treatment and never more than 4 weeks before the beginning of the treatment.

The same method of assessment and the same technique will be used whenever possible to characterize each identified and reported lesion at baseline and during follow-up. Imaging-based evaluation is preferred to evaluation by clinical examination when both methods have been used to assess the antitumor effect of a treatment. When necessary, the tumor assessment method may be a combination two methods (clinical lesion measurement for a dermal metastasis + CT scan for a liver metastasis), if the investigator feels this is the most accurate way to assess the tumors.

CT scans with contrast are preferred over PET/CT scans, but PET/CT scans are acceptable in patients who have relative contraindications to IV contrast, at the discretion of the treating investigator.

**Conventional CT and MRI-** These techniques will be performed with cuts of 10 mm or less in slice thickness contiguously. Spiral CT will be performed using a 5 mm contiguous reconstruction algorithm. This applies to tumors of the chest, abdomen, and pelvis.

**Clinical lesions-** Clinical lesions will only be considered measurable when they are superficial (e.g., skin nodules and palpable lymph nodes). In the case of skin lesions, documentation by color photography, including a ruler to estimate the size of the lesion.

**Chest x-ray-** Lesions on chest x-ray are acceptable as measurable lesions when they are clearly defined and surrounded by aerated lung. However, CT is preferable.

**Ultrasound (US)-** US will not be used to measure tumor lesions. US might be used, at the discretion of the investigator, to confirm the complete disappearance of superficial lesions assessed by clinical examination.

**Tumor markers-** Tumor markers (e.g. LDH) alone will not be used to assess response. If markers are initially above the upper normal limit, they must normalize for a patient to be considered in complete clinical response.

**Cytology, histology-** These techniques may be used to differentiate between partial responses (PR) and complete responses (CR) if necessary and determined by the investigator. Cytological confirmation of the neoplastic origin of any effusion that appears or worsens during treatment when the measurable tumor has met criteria for

response or stable disease is mandatory to differentiate between response or stable disease (an effusion may be a side effect of the treatment) and progressive disease.

### RECIST Response Categories

#### Evaluation of Target Lesions

Complete Response (CR):	Disappearance of all target lesions
Partial Response (PR):	At least a 30% decrease in the sum of the longest diameter (LD) of target lesions, taking as reference the baseline sum LD.
Progressive Disease (PD):	At least a 20% increase in the sum of the LD of target lesions, taking as reference the smallest sum LD recorded since the treatment started or the appearance of one or more new lesions. In addition to the relative increase of 20%, the sum must also demonstrate an absolute increase of at least 5 mm. (Note: the appearance of one or more new lesions is also considered progression).
Stable Disease (SD):	Neither sufficient shrinkage to qualify for PR nor sufficient increase to qualify for PD, taking as reference the smallest sum LD since the treatment started.

